5.2 Documentation Convention

The statistical analyses described in this SAP as well as production of tables, listings and figures will be performed using SAS[®], version 9.4 or higher (SAS Institute, Cary, NC). Additional statistical software may be used as needed.

5.3 Verification of Results

All tables, listings, and graphs will be verified and reviewed before considered final. The verification process will ensure that the numbers are produced by a statistically valid method and that the execution of the computations is correct. Qualified statisticians or statistical programmers employed by the DCRI (an affiliate of the Duke University School of Medicine) who have not been previously involved in the production of the original programming will perform the verification procedures. Methods of verification will include independent programming, prior to issuance of the draft statistical report, of all analysis datasets/ADaM and comparison to data listings. Tables, listings and graphs will be reviewed for accuracy, consistency with this analysis plan, consistency within tables/listings/graphs, and consistency with corresponding output. Once verification is complete, all documentation of the verification process will be filed in a statistical programming documentation notebook as required by the Statistical Standard Operations Procedures of the DCRI.

5.4 Handling of Missing Data

Efforts will be made to minimize the occurrence of missing data. However, the general approach will be to use only data which are complete with regard to the variable(s) and timepoint(s) being analyzed for descriptive summaries, or for the evaluation of safety and efficacy endpoints. In the case of a patient withdrawing or being lost (unrelated to documented AE or SAE), the denominator for rates of AE and SAE occurrence will remain as the complete Safety Population.

6 ANALYSIS POPULATIONS

Randomized population: All subjects who were enrolled and randomized in the study will be included in the analysis population for evaluating efficacy. This population will be used for analyses of efficacy.

Safety population: All subjects who receive at least one dose of study drug (solithromycin or active comparator) will be included in the analysis population for evaluating safety. This population will be used for analyses of safety.

PK population: All subjects who receive at least one dose of solithromycin (regardless of randomization assignment) and had at least one evaluable PK sample will be included in the analysis population for evaluating PK.

6.1 Methods of Analysis

Intention to treat (ITT): Subjects will be grouped for analysis according to their randomized allocation (solithromycin or active comparator) and initial solithromycin cohort (Table 3) where possible, regardless of whether the allocated therapy was administered, or switched (e.g., from IV-to-oral solithromycin), and regardless of compliance, protocol deviations, withdrawal, or anything else that occurred once randomized. For efficacy analyses the ITT grouping of subjects will be applied to the randomized population. For safety analyses the ITT grouping of subjects will be applied to the safety population.

Note: Hypothetically, a subject could be randomized to one arm and switch immediately to the other arm before the first dose. However, in practice, such switching did not occur. Therefore it is reasonable for the safety analyses (restricted to the safety population) to also group patients according to their randomized treatment assignment, which will be equivalent to grouping them according to the treatment that they initially received after being randomized.

7 SUBJECT DISPOSITION

This analysis will be performed on the randomized population. The number of subjects receiving any amount of study drug (safety population), completing study drug administration, number who withdrew from the study or discontinued from study drug early, and the number who completed the trial will be summarized by treatment arm, by age group, and by treatment arm stratified within age group. The timing and reasons for early discontinuation of study drug and/or withdrawal from the study will be summarized. The number of subjects with major protocol deviations will be summarized and listed. Additionally, a summary will be provided of subjects enrolled and randomized in each country.

8 DEMOGRAPHICS AND BASELINE CHARACTERISTICS

This analysis will be performed on the safety population. Demographic and baseline characteristics including age, sex, height, weight, race, and ethnicity, are evaluated prior to initiation of study drug. Demographic and baseline characteristics will be summarized with descriptive statistics by randomized treatment arm, and consolidated age group.

9 STUDY DRUG ADMINISTRATION

Study drug administration will be summarized in the safety population, by treatment arm, and by treatment arm stratified within consolidated age group. Subjects randomized to solithromycin will also be presented by age group and formulation. Summaries will include a frequency distribution of number of days of drug administration, summary statistics for solithromycin daily dosing amount, and frequency of active comparator antibiotics. Aggregate summaries of treatment discontinuation will be presented. For solithromycin, a subject will be considered to be prematurely discontinued if drug dosing ceases with <5 days on drug for patients starting on PO therapy, and <7 days on drug for patients starting on IV therapy. For active comparator a subject will be considered to be prematurely discontinued if drug dosing ceases with <5 days on drug, or if discontinuation is precipitated by occurrence of an AE. For the purpose of counting days on drug, any date which contains at least a partial dose will be counted. In earlier versions of the protocol (versions 1.0-2.0), 5 to 7 days of solithromycin IV therapy was allowed. For patients enrolled under those protocol versions, premature discontinuation will be determined as <5 days on drug.

For solithromycin subjects, study drug exposure information will be listed, including administered weight-adjusted dose (mg/kg), start and stop date, number of days of dosing, number of days dosing required by protocol which was in effect at the site at the time, loading dose information if applicable, and formulation. For active comparator subjects, details about the active comparator (drug name, dose, dosing frequency), the start date/stop date, and number of days of dosing will be listed.

10 DATA ANALYSIS

10.1 Safety Evaluations

New events that occur or pre-existing conditions that worsen through frequency or intensity will be reported as AEs or SAEs. The investigator will provide date of onset and resolution, intensity, frequency, action(s) taken, changes in study drug dosing, relationship to study drug, and outcome. Laboratory determinations performed by local laboratories including hematology values (hemoglobin, hematocrit, WBC count with differential, and platelet count) and serum chemistry values (blood urea nitrogen [BUN], calcium, serum creatinine, potassium, sodium, AST, ALT, alkaline phosphatase, total and direct bilirubin, and albumin) are required by the protocol within 72 hours prior to the first dose, and on the last day of study drug. In addition, investigators are asked to make every effort to obtain safety labs (to include aspartate aminotransferase, alanine aminotransferase, alkaline phosphatase, total and direct bilirubin, and white blood cell count with differential) 72 hours (± 24 hours) after the first dose, at the Day 16 and Day 28 post-randomization visits (implemented in Protocol version 3.0).

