In the Phase 3 IV to oral CABP study, 5 (1.2%) patients in the solithromycin group and 7 (1.6%) patients in the moxifloxacin group died during the study. None of the SAEs resulting in death was considered related to study drug. A total of 30 (6.9%) patients in the solithromycin group and 23 (5.4%) patients in the moxifloxacin group reported at least 1 non-fatal SAE. Only 3 SAEs were considered related to study drug by the investigators (urticaria and anaphylactic reaction in 1 patient each in solithromycin and anaphylactic reaction in 1 moxifloxacin patient). The most frequently reported infusion site related TEAEs were infusion site pain (10.4%), infusion site phlebitis (10.0%) and infusion related reaction (6.5%). Infusion site related TEAEs were mostly mild or moderate in intensity and infrequently led to discontinuation of study drug or withdrawal from the study (in 1 moxifloxacin and 10 solithromycin patients). Apart from infusion site related events, the most common AEs observed in patients receiving solithromycin were diarrhea (5.9%) and headache (4.2%).

In the adolescent oral phase 1 study (CE01-119), 12 AEs were reported, of which 9, including 1 SAE (limb abscess), were unrelated to solithromycin. Three subjects had AEs related to study drug: 2 separate episodes of mild headache and 1 episode of increased transaminases ($<3\times$ ULN).

The most common AEs reported after multiple IV doses were general disorders and administrative site conditions (infusion-related pain) followed by nervous system disorders and vascular disorders (phlebitis), with the majority mild in severity.

Solithromycin, like most antibiotics and like all macrolide antibiotics, has been associated with hepatic aminotransferase elevations. In the pooled Phase 3 CABP trials, ALT elevations to $>3\times\text{ULN}$, $>5\times\text{ULN}$ and $>10\times\text{ULN}$ were seen in 7.2%, 2.4% and 0.1% of solithromycin recipients compared to 3.6%, 1.0% and 0.2% of moxifloxacin recipients. Elevations of ALT to $>3\times\text{ULN}$ were 5.4% in the oral study and 9.1% in the IV to oral study. These elevations were typically asymptomatic, not associated with bilirubin elevation and readily reversible, with improvement in many cases seen during continued dosing. There have been no Hy's Law cases.

Multiple lines of evidence point to an exposure-response relationship for ALT elevation with solithromycin.

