12.1.1.1 Reporting of SAEs

All SAEs must be reported to APCER Life Sciences preferably by email within 24 hours of the site's knowledge of the event. APCER contact information:

APCER Email: [contact]

[contact]

[contact]

Amendment #2 16 December 2016

Rationale for Amendment

Amendment 2 incorporates additional safety laboratory evaluations along with new and updated dosing information for all 3 formulations of solithromycin.

Safety laboratories, including ALT, AST, ALP, total and direct bilirubin, and eosinophil count have been added at 72 hours (± 24 hours), Day 16 (± 4 days), and Day 28 (± 4 days). The Day 28 (± 4 days) visit evaluates safety laboratories approximately 3 weeks after completion of dosing, and replaces the Day 36 (± 4 days) visit. Data pertaining to liver laboratory evaluations will be reviewed on a regularly scheduled basis (Section 12.1.3) and presented to the DMC.

Solithromycin suspension dosing information, including the dosage rationale, has been added for all age groups. The IV dose has been updated to 8 mg/kg (maximum 400 mg) for all age groups based on additional Phase 1 pediatric PK data. PK/PD simulations based on adult CABP patient data have been reassessed following an FDA recommendation to remove the loading dose on the first oral dosing day after IV administration; the loading dose did not appear to be required for efficacy but did increase the potential for ALT elevations and could be associated with dosing errors. Consequently, the oral loading dose after IV dosing has been replaced by the daily oral maintenance dose (10 mg/kg; maximum 400 mg). A loading dose will be employed only on the first day of oral only dosing (20 mg/kg; maximum 800 mg).

The duration of dosing with solithromycin will be 5 days with oral only dosing, and 7 days with IV only or IV to oral dosing; previously the duration was 5 to 7 days for all formulations. Five-day oral and 7-day IV and IV to oral regimens of solithromycin were demonstrated to be non-inferior to moxifloxacin in the Phase 3 adult pneumonia studies (CE01-300 and CE01-301). Comparator duration of dosing will continue to be per standard of care.

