3.3 Sample Size and Randomization

Approximately 400 subjects ≥ 2 months to 17 years of age inclusive, with CABP will be enrolled. Subjects will be randomized (3:1) into two groups: solithromycin (N~300) or comparator (N~100). Randomization will be stratified by the following age groups:

- Age Group 1: Adolescents from 12 years to 17 years, inclusive
- Age Group 2: Children from 6 years to <12 years
- Age Group 3: Children from 24 months to <6 years
- Age Group 4: Infants from ≥ 2 months to <24 months

A minimum of 40 subjects will be included in each age group. Approximately 20% of subjects will be enrolled in the United States. Enrollment will occur simultaneously for all age groups for which information to inform the dosing regimen is available.

The sample size of 300 in the solithromycin group is based on the ability to observe an SAE at a frequency higher than 1% (see Table 1).

Table 1 Probability of Observing at Least 1 Subject with a Serious Adverse Event

Number of subjects	Possible Serious Adverse Event Incidence with 5 Days of Dosing				
	0.1%	0.25%	0.5%	1%	2%
100	0.095	0.22	0.39	0.63	0.87
200	0.18	0.39	0.63	0.87	0.98
300	0.26	0.53	0.78	0.95	>0.99

In addition, this sample size will provide reasonable estimates and 95% confidence interval (CI) for safety. If 1 subject has an AE, then the 95% CI (exact binomial) for incidence of that AE within the subject population of 300 subjects is 0.01%, 1.8% (see Table 2).

Table 2 Proportion of Subjects with Adverse Events and 95% CI

Number of events	Proportion	95% CI
0	0	0, 0.012
1	0.003	0.0001, 0.018
2	0.007	0.001, 0.024
3	0.010	0.002, 0.029

The above estimates assume that all 300 subjects assigned to the solithromycin arm will be evaluable for safety and do not account for the possibility that a subject may be excluded from the safety analysis, for example because she/he did not receive any study drug, or withdrew consent prior to completing follow up evaluations for safety.

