		Treatment Days up to Last Day of Treatment ^b	Last Day of Treatment (+48 hours)	Day 16 Post Randomization ^{c, d} (±4 days)	Day 28 Post Randomization ^d (±4 days)
Serious adverse event assessment	X	X	X	X	X
Clinical outcomes and symptom assessments: Early Clinical Response, End of Treatment, and Follow-Up Post Treatment ^f	X	X ^u	X ^v	X ^w	

- a Screening/baseline can occur up to 72 hours prior to randomization. Standard-of-care laboratory data and radiological imaging from up to 72 hours prior to randomization may be used as screening procedures. Screening/baseline and first day of treatment may be the same day.
- b Treatment period is 5 to 7 days for solithromycin and 5 to 10 days for comparators. These assessments and procedures may be done prior to Day 3 if the subject is discharged from the hospital before Day 3.
- c Record vital signs for each day available. Physical examinations should be recorded from baseline and the Day 3 to 4 visit (early clinical outcome assessment) and at the Last Day of Treatment visit.
- d Every effort should be made to bring the subject back. If the subject is unable or unwilling to return, the AEs/SAEs must be collected via telephone/other media.
- e Vital signs taken at the closest time post-drug administration should be noted. If vital signs following drug administration are not available, record the first value of the day.
- f Screening chest x-ray does not need to be repeated if a standard-of-care chest x-ray was performed within 72 hours of randomization. Subjects that are outpatient and starting on oral therapy do not need a screening x-ray.
- g Local laboratory; includes hemoglobin, hematocrit, white blood cell count with differential, platelet count, blood urea nitrogen, calcium, serum creatinine, potassium, sodium, aspartate aminotransferase, alanine aminotransferase, alkaline phosphatase, total and direct bilirubin, and albumin.
- h A separate study sample is not required if safety labs above are obtained at baseline per standard of care. If multiple laboratory tests are obtained within 72 hours of randomization, record test results closest to randomization.
- i Every effort should be made to obtain safety labs to include aspartate aminotransferase, alanine aminotransferase, alkaline phosphatase, total and direct bilirubin, and white blood cell count with differential. A separate study sample is not required if safety labs above are obtained within the visit window per standard of care.

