10.3.2 Laboratory Data

Descriptive statistics will be generated for post-baseline abnormal laboratory data, such as hematology and serum chemistry values. Additionally, shift tables will be presented. The shift tables tabulate the number of lab values determined to be “Normal” and “Abnormal” at baseline and post-baseline timepoints. The classifications on shift tables will categorize lab values as “Normal” when they are in an acceptable range, using a combination of clinician judgment specific to each lab test, and the local lab reference ranges (see below). Laboratory values outside the normal range will be graded on the Labs Listing as 1x, 2x, 3x, 5x or 10x the upper limit (or .5x, 1x the lower limit) of normal value based on appropriate increases or decreases. Lab tests reflective of liver toxicity (ALT, AST, and Total and Direct Bilirubin) will be further summarized in terms of the most extreme values and largest increases from baseline observed from the start of study drug through Day 16 Post-Randomization (± 4 days). Laboratory data will also be summarized graphically to show the magnitude and changes in individual subject values over time relative to normal ranges.

Laboratory Name	Clinically Pertinent Normal Range
Blood Urea Nitrogen [BUN]	(0, Site Specific ULN)
Calcium	(Site Specific LLN, Site Specific ULN)
Serum Creatinine	(0, Site Specific ULN)
Potassium	(Site Specific LLN, Site Specific ULN)
Sodium	(Site Specific LLN, Site Specific ULN)

AST	(0, Site Specific ULN)
ALT	(0, Site Specific ULN)
Alkaline Phosphatase	(0, Site Specific ULN)
Total Bilirubin	(0, Site Specific ULN)
Direct Bilirubin	(0, Site Specific ULN)
Albumin	(Site Specific LLN, ∞)
Hemoglobin	(Site Specific LLN, ∞)
Hematocrit	(Site Specific LLN, ∞)
WBC Count	(Site Specific LLN, Site Specific ULN)
Platelet Count	(Site Specific LLN, Site Specific ULN)
Neutrophils	(Site Specific LLN, Site Specific ULN)
Lymphocytes	(Site Specific LLN, Site Specific ULN)
Monocytes	(Site Specific LLN, Site Specific ULN)
Eosinophils	(Site Specific LLN, Site Specific ULN)
Basophils	(Site Specific LLN, Site Specific ULN)
C-reactive protein	(0, Site Specific ULN)
Procalcitonin	(0, Site Specific ULN)

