14.4 Safety Data

Table 14.4.1	Proportion of Subjects Experiencing a Treatment Emergent Adverse Event or Discontinuing Study Drug Due to Related Adverse Event – By Treatment Arm and Age Group
Table 14.4.1.1	Proportion of Subjects Experiencing a Treatment Emergent Adverse Event or Discontinuing Study Drug Due to Related Adverse Event – By Treatment Arm, Age Group, and Formulation
Table 14.4.2	Overview of Adverse Events – By Treatment Arm, Consolidated Age Group, and Drug Route
Table 14.4.2.1	All Treatment Emergent Adverse Events by System Organ Class and Preferred Term – By Treatment Arm, Consolidated Age Group, and Drug Route
Table 14.4.2.1.1	Treatment Emergent Adverse Events by System Organ Class and Preferred Term, Excluding Infusion Site Adverse Events – By Treatment Arm, Consolidated Age Group, and Drug Route
Table 14.4.2.1.2	Treatment Emergent Infusion Site Adverse Events by System Organ Class and Preferred Term – By Treatment Arm, Consolidated Age Group, and Drug Route
Table 14.4.2.2	Overview of Serious Adverse Events – By Treatment Arm, Consolidated Age Group, and Drug Route
Table 14.4.2.3	Treatment Emergent Serious Adverse Events by System Organ Class and Preferred Term – By Treatment Arm, Consolidated Age Group, and Drug Route

Table 14.4.3	Shift from Baseline to Worst Post-Baseline Value: Hematology Tests – By Treatment Arm
Table 14.4.3.1	Abnormal Laboratory Results Summary: Hematology Tests – By Treatment Arm
Figure 14.4.3.2	Worst Post-Baseline vs Baseline Laboratory (Scaled by Normal Values): Hematology Tests – By Treatment Arm
Figure 14.4.3.3	Worst Post-Baseline vs Baseline Laboratory (Scaled by Normal Values): Hematology Tests – By Solithromycin Consolidated Age Group and Drug Formulation
Table 14.4.3.2	Shift from Baseline to Worst Post-Baseline Value: Chemistry Tests – By Treatment Arm
Table 14.4.3.2.1	Abnormal Laboratory Results Summary: Chemistry Tests – By Treatment Arm
Figure 14.4.3.2.2	Worst Post-Baseline vs Baseline Laboratory (Scaled by Normal Values): Chemistry Tests – By Treatment Arm
Figure 14.4.3.2.3	Worst Post-Baseline vs Baseline Laboratory (Scaled by Normal Values): Chemistry Tests – By Solithromycin Consolidated Age Group and Drug Formulation
Table 14.4.3.2.4	Summary of Liver Function Tests – By Treatment Arm
Table 14.4.3.2.5	Summary of Liver Function Tests – By Solithromycin Consolidated Age Group and Drug Route
Figure 14.4.4	Summary Plot of Vital Signs – By Treatment Arm

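### The SAP summarises worst liver values by age group and route, but the number of scheduled liver tests changed at protocol version 3.0, and version is tied to age and formulation

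*SAP*

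**What the plan says.** SAP 10.1 states that the laboratory tests "are required by the protocol within 72 hours prior to the first dose, and on the last day of study drug". It then asks for added liver tests at 72 hours (±24) and "at the Day 16 and Day 28 post-randomization visits (implemented in Protocol version 3.0"). These are best effort; note i to SAP Table 4 reads "Every effort should be made to obtain safety labs to include aspartate aminotransferase, alanine aminotransferase, alkaline phosphatase, total and direct bilirubin". The Amendment 2 rationale in Protocol Appendix A dates the change: "Safety laboratories, including ALT, AST, ALP, total and direct bilirubin, and eosinophil count have been added at 72 hours", with Day 16 and Day 28 named alongside.

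SAP 10.3.2 says that ALT, AST and total and direct bilirubin are "further summarized in terms of the most extreme values and largest increases from baseline observed" from the start of drug through Day 16 (±4). Table 14.4.3.2.5 is titled "Summary of Liver Function Tests – By Solithromycin Consolidated Age Group and Drug Route". Figure 14.4.3.2.3 plots worst post-baseline chemistry against baseline, by solithromycin consolidated age group and formulation, with no end day.

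On enrolment, SAP 3.3 says "Enrollment will occur simultaneously for all age groups for which information to inform the dosing regimen is available". SAP 9 gives children enrolled under versions 1.0-2.0 their own rule for premature discontinuation. No section gives such a rule for laboratory data; SAP 5.4 uses whatever data are available.

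**The concern.** A maximum, or a largest increase, depends on how many times and when a child was tested. Columns with different testing schedules can therefore differ in worst values when the underlying risk is the same.

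Timing adds to this. Protocol 5.2.4.1 describes the adult ALT rises as "readily reversible, with improvement in many cases seen during continued dosing", so a child tested only on the last day can miss a peak that a 72-hour test would have caught.

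Liver enzymes are this drug's known laboratory signal: in the pooled adult Phase 3 trials, ALT exceeded 3x ULN in 7.2% on solithromycin and 3.6% on moxifloxacin. Readers will look in Table 14.4.3.2.5 and Figure 14.4.3.2.3 for an age or route pattern, and a pattern produced by the testing schedule would mislead them. This would hold even if the doses had never changed between versions.

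**Working it through.** The plan states no figure on testing frequency. Its one sample-size figure (0.95 for seeing at least one SAE at 1% incidence in 300) reproduces as 1 − 0.99^300 = 0.951, but does not bear on this point.

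**Step 1: scheduled post-baseline liver tests, by version and window**

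| Window | Versions 1.0-2.0 | Version 3.0 on |
|---|---|---|
| Through end of therapy (Protocol 14.1.3) | 1 (last day) | 2 (72 h, last day) |
| Through Day 16 ±4 (SAP 10.3.2) | 1 | 3 (72 h, last day, Day 16) |
| No end day (Figure 14.4.3.2.3) | 1 | 4 (adds Day 28) |

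The SAP 10.3.2 window closes by Day 16 + 4 = Day 20. The Day 28 visit opens at Day 28 − 4 = Day 24, so it lies outside. The counts for version 3.0 are maxima, because the added tests are best effort.

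**Step 2: who can be on the short schedule.** The superseded dosing tables in Appendix A, used here only to date the change, give solithromycin doses before Amendment 2 for 12-17 year capsules, 12-17 year IV and (from Amendment 1) 6 to <12 year IV. Every other cell was still to be determined, including all suspension and everything under 6 years. With enrolment limited to age groups that had dosing information, any version 1.0-2.0 solithromycin children belong to the 6-17 year column and started on capsules or IV.

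**Step 3: possible size (illustration only).** Two assumptions are not in the documents: the share f of the older column enrolled before version 3.0, taken as 0.25 to 0.75, and full completion of the added tests. The adult 7.2% is a stand-in.

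*(a) Test count.* Treat 7.2% as the chance per test of ALT >3x ULN. With independent tests, P(worst of 3 >3x ULN) = 1 − (1 − 0.072)^3 = 20.1%. With a latent-normal within-child correlation of 0.5 it is 16.4%, and at 0.8 it is 12.9%. The older column shows f × 7.2% + (1 − f) × P3; the younger shows P3.
- f = 0.5, independent: older 13.6%, younger 20.1%, ratio 1.47.
- f = 0.5, correlation 0.8: older 10.0%, younger 12.9%, ratio 1.28.
- Over f = 0.25 to 0.75 and correlation 0 to 0.8, the ratio runs from 1.12 to 1.93.

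*(b) Missed peaks.* Treat 7.2% as the true share of children with a peak, all seen on the fuller schedule, and let the last-day test catch a fraction s = 0.5 to 0.75 (assumed). The older column shows 7.2% × [1 − f(1 − s)].
- f = 0.75, s = 0.5: 7.2% × 0.625 = 4.5%, ratio 7.2/4.5 = 1.60.
- f = 0.25, s = 0.75: 7.2% × 0.9375 = 6.75%, ratio 1.07.

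**Step 4: available precision.** SAP 2 puts final enrolment below a quarter of 400, so below 100. At 3:1 that is fewer than about 75 on solithromycin, or about 37 per age column if split evenly (assumed). The largest shift in (b), 2.7 points, is about 0.027 × 37 = 1.0 child. For 3 of 37 (8.1%) the exact 95% interval is 1.7% to 21.9%.

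**The case against.** The strongest reply is that these outputs are descriptive. No test or between-column estimate is planned, the columns are very small, the analyses were deliberately curtailed after early termination, all chemistry values are listed (Listing 16.2.8.2), and individual values are to be plotted over time. The bias could amount to about one child in a column. This all stands and limits the importance of the point. It does not remove it: no listed table shows how many children were tested in each window, so a reader would have to rebuild that from the listing.

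The documents do not support several stronger readings that a reader might infer:

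- **Every child under 6 had the full schedule.** The added tests are best effort, and Protocol 10.4.1.1 caps research blood at 4 to 5 mL below 2 years and 3 mL/kg below 7 kg. Completion may be poorest in the youngest, which would shrink the contrast.
- **Hospital stay inflates the IV column.** Standard-of-care labs are recorded if done, and inpatients and outpatients are both eligible. Nothing says that inpatients had more liver tests or were mostly IV starters. Any such effect would oppose that of early IV children having fewer scheduled tests.
- **The arm comparison is biased in the same way.** Children were randomized 3:1 within age strata over the same period, so the version mix should be similar by arm. Unscheduled testing and treatment length could still differ in an open-label trial. The shift tables are by arm only.

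**Conclusion.** The concern holds for the contrasts by age and by route or formulation within solithromycin. Scheduled liver tests differ one versus three by protocol version in the most-extreme summary, and up to one versus four in Figure 14.4.3.2.3. Version is tied to age and formulation, and the SAP has no laboratory rule to match the one it wrote for discontinuation.

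If the added tests were obtained, worst values in the 6-17 year column tend to be understated relative to the younger column. The actual size cannot be computed, because neither enrolment per version nor completion of the added tests is given. The illustrative ratios of 1.07 to 1.93 rest on the assumptions in Step 3. For route, no net direction can be stated. The change is worth making because the outputs concern the drug's main laboratory signal and the correction is small.

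**What to change.** In SAP 10.3.2 and Table 14.4.3.2.5:

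1. Show, in every column, the number of children with a liver test in each scheduled window: 72 h, last day (+48 h), Day 16 and Day 28.
2. Add an age-group and route summary of value and change from baseline that uses one value per child: the last-day-of-treatment (+48 h) test, required in all versions. The scheduled count is then one versus one. Note that its study day differs by route (Day 5 for oral starters and Day 7 for IV starters in SAP 3.4) and is earlier for children who stop early. It must be the last-day value itself: a worst value up to the last day would still let the 72-hour test count for version 3.0 children only.
3. Keep the worst-value summary of all recorded tests as the safety capture. Footnote it, and Figure 14.4.3.2.3, as not comparable across age, route or formulation columns, because testing differed by protocol version and by standard-of-care labs.

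The cost is SAP wording and a few table rows from data already collected. The last-day summary does not capture earlier or later peaks, which is why item 3 keeps the full capture.
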